Study Objective: To evaluate the efficacy, safety, and tolerability of 2 doses of ubrogепant (50 mg and 100 mg) compared to placebo for the acute treatment of a single migraine attack

Clinical Hypotheses:

1. At least 1 ubrogепant dose is superior to placebo in the acute treatment of migraine.
2. Ubrogепant is safe and tolerable.

Study Design

Structure: Multicenter, randomized, double-blind, placebo-controlled, parallel-group, single attack study; randomization to placebo, ubrogепant 50 mg, or ubrogепant 100 mg.

Duration: The study includes a screening period of up to 14 days prior to randomization, a 60-day period in which to treat a single migraine attack, and a 4-week follow-up period.

Study Treatment Groups: Ubrogепant 50 mg, ubrogепant 100 mg

Controls: Ubrogепant placebo

Dosage/Dose Regimen: Study participants will have up to 60 days to treat a single qualifying migraine attack of moderate or severe headache pain intensity at home. Patients have the option to take a second dose of investigational product (IP) or rescue medication if the patient has either a nonresponding migraine or a migraine recurrence.

[REDACTED]

[REDACTED]

[REDACTED]

Study Population Characteristics

Number of Patients: Approximately 1650 patients will be randomized (550 per treatment arm)

Condition/Disease: Migraine with or without aura

Key Inclusion Criteria: To be eligible for study participation, patients must be 18 to 75 years of age (inclusive), have a history of migraine with or without aura for at least 1 year consistent with a diagnosis according to the International Classification of Headache Disorders criteria, 3rd edition, beta version (ICHD-3 beta, 2013) and experience between 2 to 8 migraine attacks with moderate to severe headache pain in each of the 3 months prior to Screening (Visit 1).

Key Exclusion Criteria: [REDACTED]

Response Measures

Efficacy: Rating of headache severity, absence or presence of migraine-associated symptoms, use of rescue medication, use of optional second dose, and recurrence of headache pain

[REDACTED]

General Statistical Methods and Types of Analyses: The efficacy analyses will be based on the Modified Intent-to-treat (mITT) Population. The last observation carried forward (LOCF) approach will be used to impute missing posttreatment values. Baseline for efficacy is defined as the last nonmissing efficacy assessment before the initial dose of study treatment. For each primary variable, the observed response proportions will be provided by treatment group. The primary efficacy variable of pain freedom at 2 hours after the initial dose will be analyzed using a logistic regression model with categorical terms for treatment group, historical triptan response (triptan responder, triptan insufficient responder, or triptan naïve), use of medication for migraine prevention (yes/no), and baseline headache severity (moderate or severe). The primary efficacy variable of absence of the most bothersome symptom at 2 hours after the initial dose will be analyzed using a similar logistic regression model with an additional categorical term for the underlying symptom that was identified as the most bothersome. The respective comparisons of the ubrogepant doses versus placebo, which are the formal tests of the efficacy hypotheses, will be conducted using the appropriate pairwise contrasts within the logistic regression model. For secondary and other efficacy endpoints related to migraine headache pain severity and/or recurrence, migraine-associated symptoms, or use of rescue medication (including the second dose of IP), the observed response proportions will be analyzed using the same methods used to analyze the primary efficacy variables. For secondary efficacy endpoints on migraine-associated symptoms, baseline presence/absence of the symptom will be included as an additional covariate for the logistic regression model. The proportion of patients reporting satisfaction with study medication at 2 and 24 hours after the initial dose, the proportion of patients able to function normally at 1, 2, 4, and 8 hours after the initial dose, and the proportion of patients assessed by the PGIC as “much better” or “very much better” at 2 hours after the initial dose will be analyzed using the same methods used to analyze the primary efficacy variables. The baseline functional disability score will also be included as a covariate for the analysis of the proportion of patients able to function normally. For the change from baseline in EQ-5D-5L index value at 24 hours after the initial dose, treatment comparisons of ubrogepant dose groups versus placebo will be performed using an analysis of covariance (ANCOVA) model with categorical terms for treatment group, baseline severity, historical triptan response, and use of medication for migraine prevention, and with the baseline EQ-5D-5L index value as a covariate. Descriptive statistics will be provided for the change from baseline in the EQ VAS score at 24 hours after the initial dose by treatment group.

[REDACTED]

[figure not shown]
[figure not shown]
[figure not shown]
[figure not shown]
[figure not shown]

Figure 1 Study Flow Diagram

1. Background and Clinical Rationale

What is Migraine and How Prevalent is It?

Migraine affects 18% of women and 6% of men in the United States with a peak prevalence occurring between the ages of 25 to 55 years. Approximately one-third of migraineurs have 3 or more migraine headaches per month, and over half report severe impairment or the need for bed rest during an attack (Lipton et al, 2007). In the United States, work loss due to migraine is estimated to cost ~ \$13 billion annually (Hu et al, 1999). Prevalence is similar in Europe, with migraine headache affecting 17.6% of women and 8% of men (Stovner and Andree, 2010). It is currently ranked by the World Health Organization as 19th among causes of disability (Katsarava et al, 2012).

Migraine is typically characterized by attacks of throbbing, unilateral headache of moderate or severe pain intensity, associated with nausea, vomiting, and/or sensitivity to light (photophobia) and sound (phonophobia). In about 25% of individuals, migraine headache may be preceded by focal neurological dysfunction (aura). Improving the diagnosis and optimizing treatments for migraine have been recognized as critically important to reduce the global burden of migraine (Katsarava et al, 2012).

Because there are no biological markers for migraine, diagnosis is based on clinical history, exam, and the exclusion of other headache disorders. Physicians apply clinical criteria to guide diagnoses and subsequent treatment. Episodic migraine is a syndrome diagnosis applied to patients with migraine (with or without aura) who have 1 to 14 headache days per month. Chronic migraine is a specific International Classification of Headache Disorders criteria, 3rd edition beta version (ICHD-3 beta) diagnosis applied to a subset of patients with ≥ 15 headache days per month (ICHD-3 beta, 2013; Katsarava et al, 2012; Olesen et al, 2006).

What is CGRP and What is its Relationship to Migraine?

CGRP (calcitonin gene-related peptide) is a neuropeptide implicated in the pathophysiology of migraine. CGRP levels in the cranial venous outflow (ie, external jugular vein) are increased during a migraine attack (Goadsby and Edvinsson, 1993) and exogenously administered CGRP has been shown to trigger migraine-like headache in migraineurs. The majority (80% to 90%) of trigeminal A δ fibers that innervate the dura contain CGRP, suggesting that these fibers may be involved in sterile neurogenic inflammation and migraine pain transmission. Furthermore, the CGRP receptor is present on human meningeal and cerebral blood vessels. These observations suggest that activation of the

trigeminovascular system, with release of CGRP, may play a key role in migraine pathogenesis and that inhibition of CGRP function may yield a novel therapeutic approach to treating migraine.

Establishment of CGRP Antagonism to Treat Migraine

The ability of CGRP antagonism to relieve pain in the acute treatment of migraine was established by using an intravenous (IV) formulation of olcegepant ([Olesen et al, 2004](#)), and replicated by Merck & Co., Inc with an oral formulation of telcagepant, a highly selective CGRP receptor antagonist (CGRP RA). In Phase 3 studies, telcagepant was superior to placebo in the primary endpoints of 2-hour pain freedom, 2-hour pain relief, and the absence of associated symptoms (photophobia, phonophobia, and nausea), as well as the key secondary endpoint of 24-hour sustained pain freedom ([Connor et al, 2009](#)). Serum alanine aminotransferase (ALT) increases were observed with telcagepant as well as with a second CGRP antagonist, MK-3207. For this reason, the development of these compounds was stopped.

What is Ubrogapant?

Ubrogapant, a novel CGRP receptor antagonist that is chemically distinct from both telcagepant and MK-3207, is now being developed for the acute treatment of migraine. Preclinical and clinical studies conducted to date for ubrogapant have shown no evidence of hepatotoxicity.

A Phase 2b clinical study was conducted, which compared 1-, 10-, 25-, 50-, and 100-mg doses of ubrogapant to placebo in the acute treatment of migraine. Overall, all the ubrogapant doses tested were well tolerated and the adverse event (AE) profile of all ubrogapant doses did not differ significantly from placebo. For the primary efficacy endpoint of pain freedom at 2 hours, ubrogapant doses of 1 and 10 mg did not differ from placebo, but doses of 25, 50, and 100 mg were better than placebo. For the primary efficacy endpoint of pain relief at 2 hours none of the ubrogapant doses differed from placebo, probably due to a high placebo response rate.

The absence of migraine-associated symptoms of photophobia, phonophobia, and nausea was assessed as key secondary endpoints. Ubrogapant doses of 50 and 100 mg were significantly better than placebo for absence of phonophobia and photophobia at 2 hours, whereas 25 mg did not differ from placebo. None of the ubrogapant doses differed from placebo for the endpoint of absence of nausea at 2 hours. Measures of sustained migraine headache relief

(2 to 24 hours and 2 to 48 hours sustained pain freedom and sustained pain relief) generally suggested that ubrogepant 50 mg and 100 mg were more effective than the 25-mg dose.

The purpose of this study will be to assess the safety and efficacy of 2 doses of ubrogepant, 50 and 100 mg, versus placebo in the acute treatment of migraine with or without aura, in a randomized, double-blind, placebo-controlled Phase 3 study.

2. Study Objectives and Clinical Hypotheses

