6.1 Efficacy Measures

Efficacy measurement assessments are based on information recorded by the patient in an eDiary.

Rating of Headache Severity

Headache severity will be subjectively rated by the patient at predefined timepoints (predose and 0.5, 1, 1.5, 2, 3, 4, 6, 8, 24, and 48 hours after the initial dose) on a scale from no pain to severe pain:

- No pain
- Mild pain
- Moderate pain
- Severe pain

Migraine Associated Symptoms

The patient will record whether the following associated symptoms were present or absent at predefined timepoints (predose and 0.5, 1, 1.5, 2, 3, 4, 6, 8, 24, and 48 hours after the initial dose):

- Photophobia
- Phonophobia
- Nausea
- Vomiting

Use of Rescue Medication

Patients will record in their eDiary any rescue medication taken within 48 hours after treating their migraine attack with IP, in addition documenting the date and time that the rescue medication was taken.

Use of Optional Second Dose and Recurrence of Headache Pain

Patients will record in their eDiary use of the optional second dose of IP due to inadequate response to their initial dose of IP. Date and time of the second dose will be reported, as well as pain severity and absence or presence of migraine-associated symptoms at the time the second dose is taken and 2 hours after taking the second dose. The incidence of recurrence in patients who had pain relief and pain freedom at 2 hours after the initial dose will be collected.

[REDACTED]

[REDACTED]

[REDACTED]

[REDACTED]

[REDACTED]

[REDACTED]

[REDACTED]

[REDACTED]

[REDACTED]

[REDACTED]

[REDACTED]

[Redacted text block]

[Redacted text block]

- [Redacted list item]

- [Redacted list item]

- [Redacted list item]

- [Redacted list item]

[Redacted text block]

[Redacted text block]

[Redacted text block]

[Redacted text block]

[Redacted text block]

[Redacted text block]

[Redacted text block]

[Redacted text block]

- [Redacted list item 1]
- [Redacted list item 2]
- [Redacted list item 3]

[Redacted text block]

[Redacted text block]

[Redacted text block]

[Redacted text block]

[Redacted text block]

[Redacted text block]

[Redacted text block]

[Redacted text block]

[Redacted text block]

[Redacted text block]

[Redacted]	[Redacted]
[Redacted]	[Redacted]
[Redacted]	[Redacted]
[Redacted]	[Redacted]
[Redacted]	[Redacted]
[Redacted]	[Redacted]
[Redacted]	[Redacted]

[Redacted text block]

[Redacted text block]

[REDACTED]

[REDACTED]

[REDACTED]

[REDACTED]

[REDACTED]

[REDACTED]

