7.2 Collection and Derivation of Efficacy Assessments

7.2.1 Primary Efficacy Variables

The coprimary efficacy parameters for the United States are as follows:

- Pain freedom (PF) at 2 hours after the initial dose, defined as a reduction in headache severity from moderate/severe at baseline to no pain, at 2 hours after the initial dose
- Absence of the most bothersome migraine-associated symptom (the most bothersome migraine-associated symptom will be identified at baseline for each patient) at 2 hours after the initial dose.

[REDACTED]

■ [REDACTED]

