7.3.1 Efficacy Analyses

7.3.1.1 Primary Efficacy Analyses

For each primary variable, the observed response proportions will be provided by treatment group. The primary efficacy variable of pain freedom at 2 hours after the initial dose will be analyzed using a logistic regression model with categorical terms for treatment group, historical triptan response (triptan responder, triptan insufficient responder, or triptan naïve), use of medication for migraine prevention (yes/no), and baseline headache severity (moderate or severe). The primary efficacy variable of absence of the most bothersome symptom at 2 hours after the initial dose will be analyzed using a similar logistic regression model with an additional categorical term for the underlying symptom that was identified as the most bothersome. If the logistic regression model fails to converge due to complete or quasi-complete separation, Firth’s penalized likelihood method (Firth, 1993) will be used. The logistic regression model will be referred to as the primary model.

The respective comparisons of the ubrogepant doses versus placebo, which are the formal tests of the efficacy hypotheses, will be conducted using the appropriate pairwise contrasts within the logistic regression model. Treatment comparisons will be based on the model-derived odds ratios and their associated 95% confidence intervals. Two-sided p-values will also be provided.

[REDACTED], the study will be considered a success if at least 1 ubrogepant dose is demonstrated to be superior to placebo on both coprimary variables after multiplicity adjustment.

[REDACTED]
[REDACTED]
[REDACTED].

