
Protocol Summary, Section 7.3.1.1 Primary Efficacy Analyses
	
Revised logistic regression model as follows: For each primary variable, the observed response proportions will be provided by treatment group. The primary efficacy variable of pain freedom at 2 hours after the initial dose will be analyzed using a logistic regression model with categorical terms for treatment group, historical triptan response (triptan responder, triptan insufficient responder, or triptan naïve), use of medication for migraine prevention (yes/no), and baseline headache severity (moderate or severe). The primary efficacy variable of absence of the most bothersome symptom at 2 hours after the initial dose will be analyzed using a similar logistic regression model with an additional categorical term for the underlying symptom that was identified as the most bothersome.
	
The treatment response on the most bothersome symptom varies according to which symptom is identified as the most bothersome

Protocol Summary, Section 7.3.1.2 Secondary Efficacy Analyses
	
Revised logistic regression model to include: For secondary efficacy endpoints on migraine-associated symptoms, baseline presence/absence of the symptom will be included as an additional covariate for the logistic regression model.
	
The treatment response on migraine-associated symptoms is different depending on whether the patient had the symptom at predose baseline.

		

Section	Revision	Rationale
	 The 'Revision' column contains two large blocks of text that have been completely redacted with black boxes. The first block is approximately 10 lines high, and the second block is approximately 5 lines high, separated by a small gap.

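### As the Protocol Summary reads, predose symptom presence is a covariate for the secondary symptom endpoints only; unless redacted text adds it, other symptom endpoints lose test power and report differently conditioned odds ratios

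*Protocol*

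**What the plan says.** The Protocol Summary (General Statistical Methods and Types of Analyses) sets a general rule: "For secondary and other efficacy endpoints related to migraine headache pain severity and/or recurrence, migraine-associated symptoms, or use of rescue medication", with second-dose use included, "the observed response proportions will be analyzed using the same methods used to analyze the primary efficacy variables". The primary pain-freedom model contains treatment group, historical triptan response, preventive medication use and baseline headache severity. It has no term for predose symptoms.

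The next sentence adds one, with a narrower scope: "For secondary efficacy endpoints on migraine-associated symptoms, baseline presence/absence of the symptom will be included as an additional covariate". Protocol 7.3.1.2 repeats it under the secondary analyses.

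The rationale in the Amendment 3 summary (Protocol 12.6) carries no such limit: "The treatment response on migraine-associated symptoms is different depending on whether the patient had the symptom at predose baseline".

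The data are available. Protocol 6.1 states: "The patient will record whether the following associated symptoms were present or absent at predefined timepoints". The list covers photophobia, phonophobia, nausea and vomiting, and the times include predose. SAP Table 5-13 defines a predose value for each of the four.

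Elsewhere in the same Summary paragraph an endpoint does receive its own baseline: "The baseline functional disability score will also be included as a covariate for the analysis of the proportion of patients able to function normally".

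**The concern.** Between two adjacent sentences the scope drops from secondary and other endpoints to secondary endpoints alone, and no reason is given. The sponsor's own argument for the term holds equally for any individual-symptom endpoint. A participant without the symptom predose is likely to be recorded as symptom-free afterwards whatever the treatment, so predose presence should be strongly prognostic.

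Two things follow if the term is left out. The treatment test has less power than the collected data allow. And because the plan reports odds ratios, a symptom endpoint analysed without the term estimates a different quantity from a secondary symptom endpoint analysed with it. Set side by side, the two could suggest a difference in effect that comes only from the model.

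**Working it through.** **No stated figure to reproduce.** No power is visible for the other symptom endpoints. Protocol Table 4 covers primary and secondary endpoints after multiplicity adjustment, so its 71% for nausea is not comparable with the single-test powers below.

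**Inputs from the documents**
- Absence of nausea at 2 hours: 59% placebo, 70% ubrogepant (Table 4). This endpoint already receives the covariate; its rates serve only to show what the term is worth.
- 550 randomized per arm (Protocol 4.1).
- Overall two-sided 5% level (Protocol 7.3); starting weight 1/2 per dose (SAP Table 5-16), hence 0.025.

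**Assumptions, not in the documents**
- 440 evaluable per arm (80% of 550).
- Nausea present predose in 50-80%; central value w = 0.60.
- Placebo absence at 2 hours of 80-95% if absent predose; central value 0.90.
- A common odds ratio in both groups; other model terms ignored.

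**1. Split the rates by predose status.** Placebo, nausea present predose: (0.59 − 0.40 × 0.90) / 0.60 = 0.3833. The common log odds ratio b is solved so that the ubrogepant rates average to 70%. This gives b = 0.625 (OR 1.87), with rates 0.5374 and 0.9439. Check: 0.60 × 0.5374 + 0.40 × 0.9439 = 0.700.

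**2. Without the covariate.**
- log OR = ln[(0.70/0.30) / (0.59/0.41)] = ln 1.62 = 0.483
- SE = √[1/(440 × 0.59 × 0.41) + 1/(440 × 0.70 × 0.30)] = 0.142
- z = 3.40

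**3. With the covariate.** Each predose group contributes information ac/(a + c), where a and c are n × share × rate × (1 − rate) for placebo and ubrogepant.
- Present: a = 62.4, c = 65.6, giving 31.99
- Absent: a = 15.8, c = 9.3, giving 5.87
- SE = 1/√37.86 = 0.163; z = 0.625/0.1625 = 3.85

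**4. Power and relative efficiency.** Power is Φ(z − 2.241) at two-sided 0.025.

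| | OR | SE(log OR) | z | Power |
|---|---|---|---|---|
| Without term | 1.62 | 0.142 | 3.40 | 87.7% |
| With term | 1.87 | 0.163 | 3.85 | 94.6% |

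Relative efficiency is (3.85/3.40)² = 1.28. A simulation of 1,500 trials fitting both models gave 88.1% and 95.3%. At 550 per arm, z scales by √(550/440) = 1.118 and power goes from 94.1% to 98.0%. At a nominal 0.05, the likelier level for endpoints outside the hierarchy, Φ(3.40 − 1.96) = 92.5% and Φ(3.85 − 1.96) = 97.0%.

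**5. Range.** The same steps over the assumed nausea ranges give relative efficiency from about 1.04 (80% present, 80% absence) to 1.77 (50% present, 95% absence). With photophobia present in 80-95% and phonophobia in 70-90%, their Table 4 rates give about 1.05-1.53 and 1.05-1.55.

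**6. Scale.** On the log-odds scale the interval is narrower without the term (SE 0.142 against 0.163). The test loses power because the unadjusted odds ratio lies closer to 1 by proportionally more than its SE shrinks. On the risk-difference scale precision does improve with adjustment: 0.0320 unadjusted, or √[(0.59 × 0.41 + 0.70 × 0.30)/440], against 0.0282 standardized over predose status.

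**The case against.** The strongest objection is that the operative text cannot be read. The protocol text after 7.3.1.2, several rows of SAP Table 5-2 (no logistic-regression row is readable), and the rows of SAP Tables 4-1 and 5-14 below the secondary endpoints are redacted. Text lost to redaction is not missing from the plan. A section headed secondary analyses would also naturally mention only secondary endpoints. This stands, and it makes the point conditional. It does not dispose of it: the Protocol Summary addresses both classes of endpoint in consecutive sentences and limits the covariate to one. SAP 5.2 reports no departure from the protocol's planned analyses, which gives no sign of a different model but proves nothing about the hidden rows.

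A reader might go further in four ways that the documents do not support:
- **That a symptom time course or a vomiting endpoint is certainly affected.** The ten postdose times in Protocol 6.1 are diary times. No readable row shows which other symptom endpoints are tested, or when.
- **That the estimates become less precise.** Protocol 7.3.1.1 fixes the scale: "Treatment comparisons will be based on the model-derived odds ratios and their associated 95% confidence intervals". On it the SE is smaller without the term. The loss is in power and comparability.
- **That the error rate is at risk.** Predose status is not affected by randomized treatment, and chance imbalance is already allowed for in the p-value and interval.
- **That the coprimary symptom endpoint has the same gap.** It does not: "the most bothersome migraine-associated symptom will be identified at baseline for each patient". Presence should then be constant, and the type of symptom is already in the model.

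It is also fair to say that the numbers borrow rates from an endpoint that already has the term, and that the gain could be trivial at the low end of the range. Both stand as limits on the size.

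**Conclusion.** The point holds as a minor, conditional one. On the readable wording, other symptom endpoints are analysed without a baseline value that the sponsor itself says matters and already collects. If the redacted SAP rows do not add it, those comparisons lose test power, and their odds ratios are not on the same footing as the secondary symptom results (1.62 against 1.87 for the same underlying rates in the illustration).

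The illustrated relative efficiency of 1.04 to 1.77 for nausea depends on assumed predose prevalence and assumed absence among those without the symptom predose. The power gain of 6.9 points (94.6 − 87.7) further assumes 440 per arm. No rates are visible for the endpoints actually concerned. The familywise procedure in SAP 5.1.1.3.4 covers only primary and secondary endpoints, so no confirmatory conclusion depends on this.

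**What to change.** First check the unredacted SAP logistic-regression row. If the term already covers all individual-symptom endpoints, only the Protocol Summary needs aligning. Otherwise change the sentence in both places to:

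> For all secondary and other efficacy endpoints on individual migraine-associated symptoms, predose presence/absence of that symptom is included as a covariate.

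Keep the Firth penalized-likelihood fallback of Protocol 7.3.1.1, since few participants without the symptom predose may report it later and separation is possible. Leave the coprimary most-bothersome-symptom model as it is.

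The cost is one sentence and one extra parameter per model. The variable is already collected and defined, and the term is already planned for the three secondary symptom endpoints.
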